#### 5.4. Rationale for Doses

The proposed mechanism of weight loss for K-757 and the K-757+K-833 combination involves enhanced secretion of satiety hormones from the gut. The satiety-promoting effects of these hormones are understood to be dose-responsive and track closely with ambient concentrations ('rapid on, rapid off'). Therefore, the target/maintenance dose-regimens in this study were selected to result in maximal and sustained satiety hormone secretion to maximize potential weight loss.

BID dosing results in sustained hormone levels throughout the dosing interval and a dose of K-757 120 mg BID + K-833 100 mg BID resulted in maximal hormone secretion and maximal rate of weight loss (Section 5.2.1). Collectively, these data support the expectation that BID co-dosing of 120 mg K-757 and 100 mg K-833 will provide the maximal weight loss attainable with this strategy.

GI intolerance (e.g. nausea, vomiting, constipation, diarrhea) is the expected result of GI hormone secretion and has been observed in Phase 1 studies.

[figure not shown]
As discussed below, titration approaches will be used in the current study to mitigate GI intolerance.

rigid dosing schedules facilitate the use of pre-packaged blister packs (see Section 13.2) which are considered critical to support participant compliance given the complexity of the double-blind, double-dummy dosing approach. As similar dosing regimens were tolerable in Phase 1, the risk that this approach will lead to a high rate of non-compliance or discontinuation is considered low. Instructions for managing GI intolerance are in Section 7.1.1.

As discussed above, BID dosing is being employed to provide maximal levels of several satiety hormones around-the-clock.

Study medication can be taken without regard to food.

Instructions on study drug administration are in Section 13.4.

## 5.5. Rationale for Study Population

The trial population will consist of individuals who are obese (BMI 30.0 to 40.0 kg/m^2, inclusive) These participants represent a clinically relevant population for pharmacotherapeutic weight management as they are at significant risk for weight related morbidities (such as hypertension, dyslipidemia, obstructive sleep apnea) and mortality and are likely to benefit from weight reduction. People with known cardiovascular disease (CVD) are excluded given the early stage of development and limited characterization of the safety profiles of the study regimens. A BMI > 40.0kg/m^2 is exclusionary to limit potential for occult CVD or other health issues that might increase the risk of participating in an early-stage clinical trial. People with T2DM are excluded due to the well-described confounding effect that improved glycemic control has on response to weight-loss interventions.

As first line treatment in weight management is lifestyle modification through a reduced-calorie diet and increased physical activity, only people who have tried but failed to attain weight loss goals with lifestyle modification will be eligible for participation.

Sex is an important response covariate with females typically achieving greater weight loss than males in obesity trials. Randomization will be stratified by sex to minimize potential bias. Weight loss trials have historically enrolled substantially more female than male participants. To ensure meaningful representation of both sexes, neither strata will be permitted to exceed 70% of total enrollment. Females of childbearing potential (FOCBP) are eligible for participation. Given the early stage of development and current lack of definitive embryo-fetal toxicology data for either K-757 or K-833, FOCBP must be using highly effective contraception with low user-dependence and undergo pregnancy testing at screening and specified timepoints during study participation.

Given the priority of avoiding spurious liver toxicity signals, excessive alcohol consumption, known history of liver disease (other than non-alcoholic fatty liver disease [NAFLD]), and excessive elevations in ALT, AST, and/or bilirubin at screening are exclusionary as specified in Section 8.2.

Observational data have suggested the possibility that agents enhancing Glucagon-like peptide-1 receptor (GLP-1R) mediated pharmacology, including GLP-1R agonists and DPP-4is, may increase the risk of acute pancreatitis, though statistically significant effects have not been identified in large cardiovascular outcomes trials (CVOTs) conducted with these agents. A recent metaanalysis of CVOT data did identify a 75% risk increase of acute pancreatitis with DPP-4is, though found no effect of GLP-1R agonists. No preclinical or clinical data generated to date have suggested that K-757 may increase the risk of pancreatitis. However, given the early stage of K-757 development, individuals with any history of acute or chronic pancreatitis are excluded from this study, as are those with excessively elevated amylase and/or lipase at screening. Markedly elevated fasting triglycerides are also exclusionary given the potential for hypertriglyceridemia to precipitate pancreatitis. Though GLP-1R agonists and DPP-4 is are commonly associated with increases in serum amylase and lipase activity, such isolated biochemical changes in the absence of suggestive signs/symptoms have not been predictive of pancreatitis. Serum lipase will be assessed at specified junctures during treatment (see Table 2). Note that protocol criteria for interrupting and discontinuing study medication for suspicion of acute pancreatitis require symptoms and/or imaging consistent with pancreatitis (see Section 8.3).

Review to Section 10.1 for discussion of prohibited and allowed concomitant medications.

Full inclusion and exclusion criteria are provided in Section 8.1 and Section 8.2, respectively.

## **6. TRIAL OBJECTIVES, HYPOTHESES AND PURPOSE**

### **6.1. Primary Objective/Hypothesis**

To assess relative (%) change from baseline in body weight after 13 weeks of treatment with K-757 alone and in combination with K-833, in comparison to placebo.

Hypothesis: At least one of the treatment arms is superior to the placebo arm in reducing body weight calculated as percentage change from baseline after 13 weeks of treatment.

### **6.2. Secondary Objectives**

1. To assess the proportion of participants achieving  $\geq 5\%$  weight loss from baseline after 13 weeks of treatment with K-757 alone and in combination with K-833, in comparison to placebo.
2. To assess the absolute change from baseline in body weight after 13 weeks of treatment with K-757 alone and in combination with K-833, in comparison to placebo.
3. To characterize the safety and tolerability of K-757 alone and in combination with K-833 over 13 weeks of treatment.

### **6.3. Exploratory Objectives**

[figure not shown]
1. To assess the change from baseline in hemodynamic parameters (systolic blood pressure, diastolic blood pressure and heart rate) after 13 weeks of treatment with K-757 alone and in combination with K-833, in comparison to placebo.
2. To assess the change from baseline in total cholesterol, low-density lipoprotein (LDL), high-density lipoprotein (HDL), and triglycerides after 13 weeks of treatment with K-757 alone and in combination with K-833, in comparison to placebo.

## 7. INVESTIGATIONAL PLAN

### 7.1. Overall Study Design

This is a randomized, double-blind, placebo-controlled 13-week study to evaluate the efficacy of K-757 alone and in combination with K-833 versus placebo in participants who are obese without T2DM. Approximately 150 participants will be enrolled and randomized (1:1:1) to receive K-757 alone, K-757+K-833, or matching placebos (Figure 4, Table 9).

**Figure 4: Study Schematic**

a Screening will occur over approximately 4 weeks.

b Refer the Dosing Table and Section 5.4.1 for study drug administration details.

c Week indicates the duration of treatment completed prior to the visit, not the week in which the visit occurs. For example, “Week 1” visit is targeted to occur on Day8 (the first day of the 2nd week of treatment).

The study will be comprised of a Screening period (up to 28 days prior to the treatment period), a 13-week double-blind Treatment period (dosing on Days 1 to 91; end-of-treatment visit Day 92), and a post-study Follow-Up period (approximately 14 days after their last dose). There will be 13 weeks of dosing (Days 1 through 91). The total duration of the study for each participant will be up to approximately 19 weeks. Randomization will be stratified by gender (male/female). Enrollment into each gender strata will be capped at 70% (ie. neither gender may exceed 70% of total enrollment).

**Table 9: Dosing Table**

Arm	Time (AM/PM)		Week			
			Week 0 (D1-7)	Week 1 (D8-14)	Week 2 (D15-21)	Week 3 through 13 (D22-92)
K-757+K-833	AM	757/833 (mg)	30/100	30/100	60/100	120/100
	PM	757/833 (mg)	pbo/pbo	30/100	60/100	120/100
K-757 alone	AM	757/833 (mg)	30/pbo	30/pbo	60/pbo	120/pbo
	PM	757/833 (mg)	pbo/pbo	30/pbo	60/pbo	120/pbo
Placebo to K-757 and K-833	AM	757/833 (mg)	pbo/pbo	pbo/pbo	pbo/pbo	pbo/pbo
	PM	757/833 (mg)	pbo/pbo	pbo/pbo	pbo/pbo	pbo/pbo

Refer to Section 5.4.1 for additional titration information.

Participants will return to the trial site at the times described in the schedule of assessments (SOA) (Table 2) to complete study procedures. During two of the on-treatment weeks when participants do not return to the trial site, the site will contact the participants by phone in order to assess study medication compliance, new concomitant medication use, and AEs.

Starting at the randomization visit (Visit 2), all participants will receive nutritional and physical activity counseling from a dietician or similarly qualified healthcare professional designated by primary investigator see Section 11.1. This counseling will occur at select visits according to the SOA (Table 2).

Safety and tolerability will be assessed in an ongoing fashion through physical examination, vital sign assessment, 12-lead electrocardiogram (ECG), clinical laboratory assessments, and collection of serious and non-serious adverse events (AEs). Specific time points are described in Table 2.

Plasma will be obtained for PK and PD at select time points during treatment (Table 2).

To mitigate mechanism-related GI intolerance, K-757 and K-833 will be titrated according to Table 9. In the combination arm and the K-757-only arm, K-757 will be titrated to the maintenance dose of 120 mg BID by Day 22. K-833 will be initiated at 100 mg QAM and will be titrated to the maintenance dose of 100 mg BID on Day 8.

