**Table 2: Study Schedule of Assessments (Continued)**

SOA													
	Screening Period	Treatment Phase by Week											ET or Post Study F/U
Visit Number	1	2 Rand.	3	4	5	6	7 g	8	9	10	11 g	12	13
Week e	~4 Weeks	Week 0	Week 1	Week 2	Week 3	Week 4	Week 5	Week 6	Week 8	Week 10	Week 12	EoT 13	Week 15
Study Day	-28	1	8	15	22	29	36	43	57	71	85	92	105
Visit Window (days)	0	0	±2	±2	±2	±2	±3	±3	±3	±3	±3	±3	±3
Efficacy and Other Endpoint Related Assessments													
Blood for K-757/K-833 PK (trough)							X			X		X	
Blood Samples for PD (trough)		X							X			X	
Body Weight	X	X				X			X			X	X
Other													
Telephone Check g							X				X		
Optional Genetic Blood Sample h												X	

a Just prior to Randomization, it will be confirmed that no excluded/prohibited medications are being taken and, in females of child-bearing potential, that the V2/Randomization urine pregnancy test is negative.

b Urinalysis at Screening only.

c Safety labs will be collected in the fasted state except at Screening.

d Serum hCG at screening and Post-study; urine hCG at randomization and Weeks 4, and 8 for females of childbearing potential. FSH test at screening only for females of non-childbearing potential due to menopause. If screening FSH test is not consistent with menopausal status, subjects may return for a serum pregnancy test and participate under requirements for females of child-bearing potential (contraception and pregnancy testing).

e Week indicates the duration of treatment completed prior to the visit, not the week in which the visit occurs. For example, the “Week 1” visit is targeted to occur on Day 8 (the first day of the 2nd week of treatment).

f Titration will occur according to [Table 9](#). On trial site visit days when laboratory safety tests are collected, participants will fast overnight and prior to study drug administration. Dosing will end with the PM dose on Day 91.

g Telephone calls at Visits 7 and 11 (Day 85) to confirm drug compliance, assess AEs, and concomitant medications.

h The optional genetic sample may be collected at any time during the study.

Abbreviations: EoT = end of treatment; ET = end of trial; FU = follow up; hCG = human chorionic gonadotropin

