### **5.3. Rationale for Study Design**

This study is designed to assess the weight loss efficacy and safety/tolerability of K-757 alone and in combination with K-833 in comparison to placebo. The overall study goal is to inform whether K-757+K-833 combination and/or K-757 alone merit further clinical evaluation as pharmacologic therapy for weight loss. Up-titration of K-757 or the combination is being used to mitigate mechanism-related GI intolerance as was observed in Phase 1 and has been consistently reported for GLP-1 analogs. No K-833-only arm is included in this first proof of concept study as neither the reported human experience with other GPR119 agonists, nor the Phase 1 experience with K-833 support the potential for K-833 monotherapy to achieve meaningful weight loss. Should weight loss with the combination of K-757+K-833 be superior to K-757 alone in the present study, future characterization of the efficacy and safety/tolerability of K-833 monotherapy may be needed to provide the necessary regulatory justification for co-development of K-757 and K-833.

The randomized, double-blind, double-dummy approach is being used to minimize the potential impact of bias on study assessments. The 13-week duration of dosing is the longest treatment duration supported by completed toxicology studies. Though 13 weeks may not be long enough

to ascertain maximal achievable weight loss, it is expected to be sufficient to determine whether placebo-adjusted weight loss in one or more of the active treatment arms is sufficient to support continued development. As detailed in Section 16.2, the sample size of 50/arm was selected to enable demonstration of the primary hypothesis of weight loss superiority of  $\geq 1$  of the active treatment arms vs. placebo. The study is not expected to be of adequate size or duration to confirm differential efficacy between the combination and K-757-alone but may provide evidence of separation.

The rationale for the study population is discussed below in Section 5.5.

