### Mandatory fasted visits:

Amongst the in-person clinic visits during the Treatment Period, V2 (randomization), V6 (Day 29), V9 (Day 57) and V12 (Day 92), subjects should come to the clinic in the fasted state because body weight and fasting lipids need to be assessed in the fasted state. These fasted visits should be scheduled in the morning and the AM dose of study medication should be taken after collection of blood. Dosing should be witnessed at these visits. Other in-person visits during the Treatment Period can be in the fasted or fed state and may be scheduled without regard to timing of study medication.

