## 11. STUDY RESTRICTIONS AND REQUIREMENTS

### 11.1. Dietary and Physical Activity Requirements and Restrictions

#### Fasting Prior to Study Visits

1. Participants must attend visits V2, V6, V9, V12, and V13 in the fasted state. These visits should be scheduled in the morning.
2. Fasting is defined as at least 8 hours before the visit without food or liquids, except for water.
3. At fasted visits, the morning doses of study medication should be withheld until blood samples have been obtained (except V12 and V13 where there is no dosing).

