#### 4.5 Per Protocol Analysis Set

The per protocol analysis set consist of all participants who completed 13-week treatment and have weight assessment at week 13 and treatment compliance >=80%. Participants who completed treatment but have week 13 assessment done more than 3 days after last dose date and participants whose weights at week 13 are collect at non-fasted state are excluded.

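### Protocol sections disagree on whether study drug is taken on Day 92 (Visit 12), and the last dose date behind several SAP rules moves with the answer

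*Protocol*

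**What the plan says.** **Sections indicating a dose on Day 92 or at Visit 12**

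- Protocol Synopsis Dosing Table and Table 9: the maintenance column is headed "Week 3 through 13 (D22-92" and has both AM and PM rows.
- Protocol Section 9.2, mandatory fasted visits: Visit 12 (Day 92) is named with Visits 2, 6 and 9. The morning dose is to follow the blood draw, and "Dosing should be witnessed at these visits". Visit 12 is not excepted.
- Protocol Section 9.2, opening paragraph: the Day 92 procedures at Visit 12 are described as post-dose.

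**Sections indicating none**

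- Protocol Synopsis and Section 7.1, repeated in SAP Section 3.1: "dosing on Days 1 to 91; end-of-treatment visit Day 92". The protocol adds "There will be 13 weeks of dosing (Days 1 through 91".
- Protocol Table 2 footnote f, repeated in SAP Appendix 1: "Dosing will end with the PM dose on Day 91".
- Protocol Section 11.1, on withholding the morning dose at fasted visits: "except V12 and V13 where there is no dosing".

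**What depends on the answer**

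- Protocol Section 5.3: "The 13-week duration of dosing is the longest treatment duration supported by completed toxicology studies".
- SAP Sections 4.5 and 5.8.1.4 leave out of the per-protocol (completer) analysis participants who completed treatment but "have week 13 assessment done more than 3 days after last dose date".
- SAP Sections 5.7.1, 5.11.1 and 5.1.6 use the last dose date for exposure, for the treatment-emergent period (2 weeks after last dose), and for the upper limit of completers' Week 13 mapping window (last dose date plus 3 days).

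**The concern.** Sections 9.2 and 11.1 both instruct sites about the same morning. One has the participant take a witnessed dose after the blood draw; the other says there is no dose. Footnote f ends dosing on Day 91, yet it sends the reader for titration to Table 9, whose last column runs to Day 92. A site cannot follow all of these.

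Two things are at stake. The first is conduct: drug may be given on a day that other sections place outside the dosing period, in a protocol that ties its dosing length to the limit of its toxicology support. The second is analysis: the SAP takes each participant's last dose date as an input, so two participants with identical Visit 12 timing could be classified differently because their sites followed different sections.

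**Working it through.** **1. The plan's own figure.** 13 weeks × 7 = 91 days, so Days 1 to 91 are exactly 13 weeks and the design text is self-consistent. Days 1 to 92 are 92 days, or 92 / 7 = 13.14 weeks. By the dosing table's own labels (Week 0 is Days 1–7), Week k covers Days 7k + 1 to 7k + 7. Week 12 is then Days 85–91, and Week 13 would begin on Day 92.

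**2. The per-protocol rule across the Visit 12 window.** Table 2 allows Day 92 ± 3, that is Days 89 to 95. Gap = Visit 12 day minus last dose day; a gap above 3 is excluded. For visits before the nominal last dosing day I assume that dosing stops the day before the visit (no dose at Visit 12) or on the visit day (the other two readings).

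| Visit 12 day | Dosing ends Day 91 | Dosing ends Day 92 | Dose given at Visit 12 |
|---|---|---|---|
| 89, 90, 91 | 1 | 0 | 0 |
| 92 | 1 | 0 | 0 |
| 93 | 2 | 1 | 0 |
| 94 | 3 | 2 | 0 |
| 95 | **4, excluded** | 3, kept | 0, kept |

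One of the seven allowed days changes status.

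**3. Other quantities tied to the last dose date**, for last dose on Day 91, on Day 92, or at a Day 95 Visit 12:

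- Exposure (last minus first + 1): 91, 92 or 95 days. The formula counts calendar days, so the 95 would not mean that drug was taken on each of Days 92–94.
- End of the treatment-emergent period (last dose + 14): Day 105, 106 or 109.
- Upper limit of completers' Week 13 mapping window (last dose + 3): Day 94, 95 or 98. SAP Section 5.1.6 does not apply these windows to scheduled visits, so this affects unscheduled weights only.
- Compliance (SAP Section 5.7.2) needs both AM and PM doses for a complete day. If a morning-only dose on Day 92 counts as a dosing day, full adherence reads 91 / 92 = 98.9% and leaves the 100% category. The 80% per-protocol threshold is not threatened.

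**4. Primary analysis.** SAP Section 5.8.1.2 uses completers' data to end of treatment and words its 3-day cut for those who discontinue. Completers' scheduled Visit 12 weights stay in the MMRM under every reading.

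**5. Size for the completer analysis.** The stated power checks out: 50 × 0.8 = 40 per arm, difference 4, SD 4 and two-sided 0.05 give 0.994, against the stated figure of above 95%. The documents do not say how many visits will fall on Day 95. Assuming 2%, 5% or 10% of 40 per arm are lost, n is 39.2, 38 or 36 and nominal power is 0.993, 0.992 or 0.989. The issue is who belongs to the set, not power.

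**The case against.** The strongest reply is that this is a labelling slip with little reach. Footnote f is exact, and the design text separates the dosing days from the end-of-treatment visit. Section 11.1 expressly excepts Visit 12. Table 2 shows no dispensing after Visit 10, and the Day 105 follow-up is 105 − 91 = 14 days after Day 91. Week 13 in the table header could simply be the visit label carried over. This shows that a single intention may exist. It does not remove the conflict: Section 9.2 is an operative site instruction with no Visit 12 exception, it also calls that day's procedures post-dose, and the documents do not say whether supply from Visit 10 would leave a dose in hand.

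The reply is right on several stronger readings that a reader might infer:

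- *Up to four extra days of dosing.* No text schedules daily dosing on Days 93–95. The tables add Day 92, and Section 9.2 describes one morning dose at the visit. Day 95 is only the latest date on which that dose could fall.
- *Exposure shown to be unsafe.* Section 5.3 speaks of 13 weeks, and the visible text gives no day count for the toxicology studies. The texts conflict; whether one further dose lacks support cannot be judged from them.
- *SAP rules undefined, or the primary result at risk.* The rules run on recorded dates under any reading, and step 4 shows that the primary analysis keeps the scheduled weights.
- *The 3-day rule is itself an error.* A per-protocol set may be stricter than a visit window. Section 5.4 describes satiety effects that closely follow hormone concentrations, so limiting time off drug is a legitimate choice.

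**Conclusion.** The contradiction stands in current text and is more than clerical, because it concerns whether a dose is given at the visit that supplies the primary endpoint. Its size is one additional dosing day (Day 92) or one morning dose at Visit 12, possibly as late as Day 95, against a stated 91-day dosing period. In the analysis it shifts exposure and the treatment-emergent period by the same amount as the last dose date, and among in-window visits it changes per-protocol status on Day 95 only. The primary MMRM is unaffected for completers' scheduled Visit 12 weights.

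This rests on two assumptions: that sites could act on Section 9.2 as written, and that the recorded last dose date reflects what was taken. No view is taken on which dosing statement is right.

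**What to change.** 1. Reconcile the Synopsis Dosing Table, Table 9 and both parts of Section 9.2 with the Synopsis and Section 7.1 design text, Table 2 footnote f and Section 11.1. All should state one last dosing day and one instruction for Visit 12, including what applies when the visit falls before or after Day 92. The result should be checked against the duration statement in Section 5.3.
2. With that settled, confirm in SAP Sections 4.5 and 5.8.1.4 whether an in-window Day 95 visit is meant to be excluded. Rewording the rule to admit every visit on Days 89–95 is optional and not required.
3. State in SAP Section 5.7.2 how a day with only a morning dose at Visit 12 would count, if that instruction is kept.

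The cost is a protocol clarification letter and a sentence or two in the SAP before database lock. Sample size, data collection and the primary model do not change.
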